# 10.10.2. Analyses of immunogenicity

The primary analysis will be based on the ATP cohort for analysis of immunogenicity. If the percent of enrolled subjects excluded from this ATP cohort is more than 5%, a second analysis based on the Total Vaccinated cohort will be performed to complement the ATP analysis.

#### 10.10.2.1. Anti-HBs antibodies

The seroprotective level for anti-HBs is  $\geq 10$  mIU/mL; The percentage of subjects with protective levels of anti-HBs ( $\geq 10$  mIU/mL) with 95% confidence interval (95% CI) will be determined at Month 14 (Clinic Visit 12). Antibody titers will be summarized by GMT with 95% CI at Month 14 (Clinic Visit 12). Antibody titers after the third dose will also be investigated using reverse cumulative curves.

#### 10.10.2.2. Anti-CS antibodies

The percentage of subjects with sero-positive levels of anti-CS (proportion of subjects with anti-CS antibody titers greater than or equal to 0.5 EU/mL) with 95% CI will be determined at Clinic Visit 12. Antibody titers will be summarized by GMT with 95%CI. Antibody titers after the third dose will also be investigated using reverse cumulative curves.

### 10.10.3. Analyses of efficacy

#### 10.10.3.1. Exploratory analysis

The exploratory endpoints will be analyzed in the Total Vaccinated Cohort and the ATP Cohort for efficacy.

For the first exploratory endpoint (time to the first clinical episode of symptomatic *P*. *falciparum* malaria defined as the presence of *P*. *falciparum* asexual parasitemia above 500 per  $\mu$ L on Giemsa stained thick blood films AND the presence of fever [axillary temperature  $\geq 37.5^{\circ}$ C] at the time of presentation), the time at risk is defined as in Section 10.9.3.1. However, the time at risk will begin at Day 0 and will end whenever one of the following conditions happen first: fits the case definition for malaria infection, loss of follow up, emigration from the study area, withdrawal, death, end of follow-up period (Clinic Visit 12, end of single blind phase). The time at risk will not be adjusted for the absences from the study area and the anti-malarial drug therapy. Vaccine efficacy will be calculated in the same manner as described in Section 10.9.3.2 using Cox regression models. Only crude estimates, not adjusted for prognostic/stratifying factors will be presented.

For the analysis of the total number of clinical episodes, the incidence of episodes (total number of episodes/person years at risk) for each group will be presented. The significance of the group effect will be assessed using Poisson regression models with random effects including the time at risk as an off-set variable. Vaccine efficacy is defined as 1-R where R is the rate ratio of clinical episodes of the RTS,S/AS02D group versus the Engerix-B group (with 95% CI). Only crude estimates, not adjusted for prognostic/stratifying factors will be presented.

Both analyses will be done including cases from the passive case detection only (see Section 5.1.16).

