- At each contact for ADI, history of fever will be recorded and axillary temperature taken; a blood sample will be taken for malaria parasite genotyping and a smear will be taken for detection of malaria parasites.

- Subjects who are symptomatic at the time of ADI contact (i.e. history of fever within previous 24 hours or axillary temperature >37.5°C) will have a blood slide read and treated within the same day if the blood slide is positive.
- Infants will be followed passively for the occurrence of clinical malaria for the duration of their participation in the study. Cases will be detected at all health facilities in the study area.
- Infection with malaria parasites is defined as *P. falciparum* asexual parasitemia > 0
- Data collection will be by conventional CRF.
- Duration of the study will be 14 months per subject.
- The final analysis of the study for all primary and secondary endpoints will take place on all data collected up to the end of the surveillance for ADI (Clinic Visit 11)
- All children will be followed for safety for a period that extends to 12 months post Dose 3. All data collected after the Final Analysis (Clinic Visit 11) will be reported in an Annex Report.
- This study is overseen by a formally constituted DSMB operating under a charter. During the vaccination phase of the study full safety reports will be sent to the DSMB at 3 points corresponding to; after 30, 60 and 100 subjects have been enrolled and have completed the first 7 days of follow-up post Dose 1 of RTS,S/AS02D or Engerix-B.
- This is the first administration of RTS,S/AS02D to infants and therefore the sample size of this Phase 1/2 safety study is limited to 200. Therefore only large differences in the frequencies of SAEs can be detected with reasonable power. The data set will be examined, comparing the rates of SAEs at the Medical Dictionary for Regulatory Activities (MedDRA) preferred term level. A sample size of 200 has the power to detect differences in the rates of safety endpoints (SAEs at the MedDRA preferred term level) as shown in the table below:

Frequency of events for Engerix-B	Frequency of events for RTS,S/AS02D	Power to detect difference (number per group equals 100)
1%	12%	80%
3%	15%	80%
5%	19%	80%
10%	26%	80%

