# Table 7Frequency of children according to the number of episodes by
treatment group (ATP Cohort for Efficacy) (Cohort 1), Malaria-026

Number of	R( N=		C( N=		Tota N= 14		
episodes per child	Value or n	%	Value or n	%	Value or n	%	p-value
0	622	83.5	586	78.7	1208	81.1	0.0508
1	99	13.3	131	17.6	230	15.4	-
2	18	2.4	25	3.4	43	2.9	-
3	6	0.8	3	0.4	9	0.6	-

R(1): RTS,S/AS02A (Cohort 1, < 24 months)/ RTS,S/AS02A (Cohort 1,  $\ge$  24 months) C(1): Prevnar and Hiberix (Cohort 1, < 24 months)/ Engerix-B (Cohort 1,  $\ge$  24 months) N=number of subjects n=number of subjects in a given category Value=value of the considered parameter %=n / Number of subjects with available results x 100 p-value: Fisher Exact test

To estimate the VE against all clinical episodes of malaria meeting the Primary Case Definition, the time at risk was adjusted using all of the criteria for the Primary Efficacy Endpoint with the addition of an exclusion period of 28 days after an episode. The adjusted VE against all clinical episodes in the ATP Cohort for Efficacy was 27.3% (95% CI 6.2% to 43.8; p=0.0143).

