# 10.9.3. Analyses of efficacy

#### 10.9.3.1. Calculation of the time at risk

For the efficacy endpoint (time to first malaria infection), the time at risk will be counted in days, and expressed as child years at risk (days/365.25).

For each subject in the Total Cohort, time at risk begins 14 days after Dose 3 for those that received Dose 3 or 2/2 months after Dose 1 (Day 75 90) otherwise. For the According to Protocol cohort, time at risk begins 14 days after Dose 3 (Amended 12 April 2005).

The time at risk will end whenever one of the following conditions happen first: fits the case definition for malaria infection, loss of follow up, emigration from the study area, withdrawal, death, end of follow-up period (Clinic Visit 11).

The time at risk will take into account absences from the study area and anti-malaria drug therapy. The monthly home visits will be used to determine any period of travel outside the study area. Absences from the study area of 2 weeks or more will be recorded in multiples of 1 week. The date of departure will be documented. Similarly, if treatment for malaria is administered, the subject will not be considered susceptible to malaria infection for the longest duration of the combination of drugs the subject could receive for this episode as follows: 28 days if received sulphadoxine-pyrimethamine, 7 days if having received chloroquine alone, 7 days if having received co-artemesinin.

If an episode is detected during a period of time not counting for the time at risk it will not be included in the analysis, however a table will be presented showing the number of such episodes not included in the analysis.

Episodes will be included in the analysis only if the child is identified properly showing his/her ID Card at the contact with the health facility and the study number is written in the OPD form. Only blood slides that complete the reading process according to SOP will be considered in the establishment of a malaria infection.

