#### 10.9.4. Exploratory analysis

The exploratory endpoints will be analyzed in the Total Vaccinated Cohort and the ATP Cohort for efficacy.

For the first exploratory endpoint (time to the first clinical episode of symptomatic *P*. *falciparum* malaria defined as the presence of *P*. *falciparum* asexual parasitemia above 500 per  $\mu$ L on Giemsa stained thick blood films AND the presence of fever [axillary temperature  $\geq 37.5^{\circ}$ C] at the time of presentation), the time at risk is defined as in Section 10.9.3.1. However, the time at risk will begin at Day 0 and no adjustments will be made for the absences from the study area and the anti-malarial drug therapy. Vaccine efficacy will be calculated in the same manner as described in Section 10.9.3.2 using Cox regression models. Only crude estimates, not adjusted for prognostic/stratifying factors will be presented.

This analysis will be done including cases from the passive case detection only (see Section 5.1.16) and including cases from both the passive case detection and the active detection of infection (ADI, see Section 5.1.17)

Note that the total number of clinical episodes will only be analyzed at the end of the single-blind phase.

The frequency of CS-specific CD4+ and CD8+ T cells will be summarized for each group at each timepoint (descriptive statistics).

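### Time at risk for the first clinical malaria episode ends at any detected parasitemia rather than at a clinical episode, so clinical episodes that follow an ADI-detected infection would not be counted

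*Protocol*

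**What the plan says.** **Endpoint.** Protocol Section 10.4 and the Synopsis define the clinical episode as asexual *P. falciparum* parasitemia above 500/µL together with axillary temperature of at least 37.5°C at presentation.

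**Annex analysis, Day 0 to Visit 12 (Section 10.10.3.1).** For time to the first such episode, time at risk "will end whenever one of the following conditions happen first: fits the case definition for malaria infection, loss of follow up", followed by emigration, withdrawal, death and Clinic Visit 12.

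**Month 6 analysis (Section 10.9.4).** Time at risk is as in Section 10.9.3.1, with these changes only: "However, the time at risk will begin at Day 0 and no adjustments will be made for the absences from the study area" or for antimalarial drugs. The end of risk is not restated, so the list in Section 10.9.3.1 applies: "fits the case definition for malaria infection, loss of follow up, emigration from the study area, withdrawal, death, end of follow-up period (Clinic Visit 11").

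**Infection.** The Synopsis and Section 3 say: "Infection with malaria parasites is defined as *P. falciparum* asexual parasitemia > 0". Under Section 5.1.17 a child counts as infected whether the parasites are found by field-worker surveillance or at a health facility. ADI visits then cease, but morbidity surveillance and monthly home visits go on.

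**Episodes outside time at risk.** Section 10.9.3.1 leaves these out of the analysis and only tabulates how many there were.

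**The concern.** For a time-to-first-event analysis, follow-up should end at the event under study or when observation stops. Here it ends at a different and more frequent event. A control infant with an afebrile positive slide in Month 4 and a febrile, high-density episode in Month 8 would be censored in Month 4, and the Month 8 episode would not count.

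The censoring is not neutral. Infection is expected to be more common in controls, and exposure drives both infection and clinical disease. The children still at risk later are the less exposed, and the selection is stronger in controls. The Cox model would then describe the hazard of clinical malaria among children with no detected infection so far, which is not the endpoint in Section 10.4.

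**Working it through.** **Inputs (Section 10.5.3).** Control attack rate over the 3-month surveillance is 75%; vaccine efficacy is 45%, so the hazard ratio is 0.55; the stated vaccine-group attack rate is 53.3%. ADI runs from Month 3 to Month 6 (Section 5.1.17) and follow-up ends at Month 14.

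**Plan's own figure.** 1 − (1 − 0.75)^0.55 = 0.5335, which reproduces 53.3%.

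**Children stopped by Visit 11.** 75% of controls and 53.3% of vaccinees. Still at risk for Months 6–14, which is 8 of the 14 months: 25% and 46.7%.

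**Mean month of infection among those infected.** Assume a constant hazard λ over the three months, λ = −ln(1 − a)/3. The mean is 3 + 1/λ − 3(1 − a)/a.
- Control: λ = 1.3863/3 = 0.4621; 3 + 2.164 − 1.000 = 4.164.
- Vaccine: λ = 0.55 × 0.4621 = 0.2542; 3 + 3.935 − 2.623 ≈ 4.31.

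**Share of person-time lost** = a × (T − mean)/T.

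| Analysis | Control | Vaccine |
|---|---|---|
| To Month 14 | 0.75 × (14 − 4.164)/14 = 52.7% | 0.5335 × (14 − 4.311)/14 = 36.9% |
| To Month 6 | 0.75 × (6 − 4.164)/6 = 23.0% | 0.5335 × (6 − 4.311)/6 = 15.0% |

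If infection is dated at the scheduled ADI visit that finds it, the 14-month losses are 51.3% and 35.9%.

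**Sensitivity to the control attack rate (14 months, exact infection times).** 50% gives 34.5% lost; 65% gives about 45%; 70% gives 49.0%; 72% gives 50.5%; 90% gives 64.5%.

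**Sensitivity to clinical risk.** The corrected rule also stops children, at their first clinical episode. The protocol gives no 14-month clinical risk, so 20%, 40% and 60% are assumed, independent of infection and equal in both arms. Measured against follow-up under the corrected rule, the control loss is 51%, 49% and 45%, and the vaccine loss is 36%, 34% and 32%. At 20% risk, 9.9 of every 20 control episodes and 12.9 of every 20 vaccine-group episodes would still be counted.

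**Limits.** The 75% and 53.3% are all first infections. Some would be first found as qualifying clinical episodes, and those children stop under either rule, so the ADI-window losses above are maxima at the planning rates. Infections found outside the window, such as a positive slide at Dose 3, would also stop time at risk. No rate is given for them and they are not counted here.

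**The case against.** The best defence is that this is a drafting slip. The phrase matches Section 10.9.3.1, where it is right for the infection endpoint. The endpoint definitions themselves are clinical and say nothing about stopping at infection, and no data are lost because surveillance continues. One could add that Section 10.10.3.1 limits its analyses to passively detected cases, so asymptomatic ADI slides might not be meant. The slip is plausible, but nothing in the protocol says so. Section 10.10.3.1 rewrote the list to move the end from Visit 11 to Visit 12 and kept infection in it. The restriction to passive detection says which cases count as events; it does not change what ends time at risk.

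A reader might infer more than the documents support:
- **That most control follow-up is lost.** It is about half of 14-month person-time, falls below half at attack rates under about 72%, and is about 23% in the Month 6 analysis. The 75% is itself a planning figure from children aged 7 to 18 months.
- **That efficacy against clinical malaria cannot be estimated.** The data would exist. The prescribed analysis simply targets something else, and neither direction nor size of bias in the efficacy estimate has been shown.
- **That the total-episodes analysis expressly stops at infection.** The stop is worded for the first-episode endpoint. The Poisson offset uses time at risk without giving another end, so the stop would apply only by inheritance.
- **That a 28-day gap between episodes is required by precedent.** Malaria-026 defined time at risk "with the addition of an exclusion period of 28 days after an episode" in its ATP analysis (Section 1.3.3.3.4), but its Day 0 ITT analysis did not adjust for previous episodes (Section 1.3.3.3.7).
- **That the ATP analysis from Day 0 must go.** Section 10.9.4 states: "The exploratory endpoints will be analyzed in the Total Vaccinated Cohort and the ATP Cohort for efficacy". The Total Vaccinated Cohort is thus already analysed, and Section 10.6.4 does not fix ATP membership at Dose 3. Dropping the ATP analysis would be a preference.

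**Conclusion.** The point holds for the first-episode clinical endpoints: expressly in Section 10.10.3.1, and by inheritance in Section 10.9.4. Followed as written, the rule would censor up to 75% of controls and 53% of vaccinees by Month 6. At most about half of control and about 36% of vaccine 14-month person-time would go (about 23% and 15% to Month 6). These sizes rest on the Section 10.5.3 planning rates, a constant infection hazard during ADI, and stops within the ADI window only. The loss is unequal between arms and tied to exposure, so the result would not estimate the stated endpoint. For total episodes the defect is a missing end of time at risk. All of these endpoints are exploratory with crude estimates; the primary safety and secondary infection analyses are untouched. The change should be made, but it is not critical.

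**What to change.** In Sections 10.9.4 and 10.10.3.1, state that time at risk for the first-episode endpoints ends at the first episode meeting the clinical case definition, or at loss to follow-up, emigration, withdrawal, death, or Visit 11 (Section 10.9.4) or Visit 12 (Section 10.10.3.1), whichever comes first. For the total-episodes analysis, state that time at risk runs to Visit 12 or earlier loss to follow-up, emigration, withdrawal or death, and does not stop at infection. Section 10.9.3.1 stays as it is for the infection endpoint.

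The cost is wording only; passive surveillance already covers the added time. In the Section 10.9.4 analysis that adds actively detected cases, ADI visits cease at first infection, so later episodes in those children would be found mainly passively. The report should say so.

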# 11. ADMINISTRATIVE MATTERS

To comply with Good Clinical Practice important administrative obligations relating to investigator responsibilities, monitoring, archiving data, audits, confidentiality and publications must be fulfilled. See Appendix B for details.

#### Appendix A World Medical Association Declaration of Helsinki

Recommendations guiding physicians in biomedical research involving human subjects

Adopted by the 18th World Medical Assembly Helsinki, Finland, June 1964 and amended by the 29th World Medical Assembly Tokyo, Japan, October 1975 35th World Medical Assembly Venice, Italy, October 1983 41st World Medical Assembly Hong Kong, September 1989 and the 48th General Assembly Somerset West, Republic of South Africa, October 1996

#### INTRODUCTION

It is the mission of the physician to safeguard the health of the people. His or her knowledge and conscience are dedicated to the fulfilment of this mission.

The Declaration of Geneva of the World Medical Association binds the physician with the words, "The health of my patient will be my first consideration," and the International Code of Medical Ethics declares that, "A physician shall act only in the patient's interest when providing medical care which might have the effect of weakening the physical and mental condition of the patient."

The purpose of biomedical research involving human subjects must be to improve diagnostic, therapeutic and prophylactic procedures and the understanding of the etiology and pathogenesis of disease.

In current medical practice most diagnostic, therapeutic or prophylactic procedures involve hazards. This applies especially to biomedical research.

Medical progress is based on research which ultimately must rest in part on experimentation involving human subjects.

In the field of biomedical research a fundamental distinction must be recognized between medical research in which the aim is essentially diagnostic or therapeutic for a patient, and medical research, the essential object of which is purely scientific and without implying direct diagnostic or therapeutic value to the person subjected to the research.

Special caution must be exercised in the conduct of research which may affect the environment, and the welfare of animals used for research must be respected.

Because it is essential that the results of laboratory experiments be applied to human beings to further scientific knowledge and to help suffering humanity, the World Medical

Association has prepared the following recommendations as a guide to every physician in biomedical research involving human subjects. They should be kept under review in the future. It must be stressed that the standards as drafted are only a guide to physicians all over the world. Physicians are not relieved from criminal, civil and ethical responsibilities under the laws of their own countries.

#### I. BASIC PRINCIPLES

- 1. Biomedical research involving human subjects must conform to generally accepted scientific principles and should be based on adequately performed laboratory and animal experimentation and on a thorough knowledge of the scientific literature.
- 2. The design and performance of each experimental procedure involving human subjects should be clearly formulated in an experimental protocol which should be transmitted for consideration, comment and guidance to a specially appointed committee independent of the investigator and the sponsor provided that this independent committee is in conformity with the laws and regulations of the country in which the research experiment is performed.
- 3. Biomedical research involving human subjects should be conducted only by scientifically qualified persons and under the supervision of a clinically competent medical person. The responsibility for the human subject must always rest with a medically qualified person and never rest on the subject of research, even though the subject has given his or her consent.
- 4. Biomedical research involving human subjects cannot legitimately be carried out unless the importance of the objective is in proportion to the inherent risk to the subject.
- 5. Every biomedical research project involving human subjects should be preceded by careful assessment of predictable risks in comparison with foreseeable benefits to the subject or to others. Concern for the interests of the subject must always prevail over the interests of science and society.
- 6. The right of the research subject to safeguard his or her integrity must always be respected. Every precaution should be taken to respect the privacy of the subject and to minimize the impact of the study on the subject's physical and mental integrity and on the personality of the subject.
- 7. Physicians should abstain from engaging in research projects involving human subjects unless they are satisfied that the hazards involved are believed to be predictable. Physicians should cease any investigation if the hazards are found to outweigh the potential benefits.
- 8. In publication of the results of his or her research, the physician is obliged to preserve the accuracy of the results. Reports of experimentation not in accordance with the principles laid down in this Declaration should not be accepted for publication.
- 9. In any research on human beings, each potential subject must be adequately informed of the aims, methods, anticipated benefits and potential hazards of the study and the discomfort it may entail. He or she should be informed that he or she is

134

at liberty to abstain from participation in the study and that he or she is free to withdraw his or her consent to participation at any time. The physician should then obtain the subject's freely-given informed consent, preferably in writing.

- 10. When obtaining informed consent for the research project the physician should be particularly cautious if the subject is in a dependent relationship to him or her or may consent under duress. In that case the informed consent should be obtained by a physician who is not engaged in the investigation and who is completely independent of this official relationship.
- 11. In case of legal incompetence, informed consent should be obtained from the legal guardian in accordance with national legislation. Where physical or mental incapacity makes it impossible to obtain informed consent, or when the subject is a minor, permission from the responsible relative replaces that of the subject in accordance with national legislation.

Whenever the minor child is in fact able to give a consent, the minor's consent must be obtained in addition to the consent of the minor's legal guardian.

12. The research protocol should always contain a statement of the ethical considerations involved and should indicate that the principles enunciated in the present Declaration are complied with.

